Cover Page

Study Protocol

Study Title: Mirror Therapy and Treadmill Training for Patients with Chronic Stroke. A Pilot Randomised Controlled Trial

Document creation date: December 12th 2014

NCT number [not yet assigned].

Identifiers: [NCT ID not yet assigned]

Study Protocol for Mirror Therapy and Treadmill Training ([name], IT Sligo, Ireland).

Research sessions will take place in the Institute of Technology Sligo, in the health science physiology lab located in the main building on campus. A total of 30 participants will be randomly assigned to one of two conditions.

Patients will verbally guide the speed of the treadmill at the beginning of each of the 12 therapy sessions and this will be adjusted by the therapist accordingly. A COSMED h/p/cosmos T170 treadmill will be for the intervention. Patients encouraged to walk at their comfortable walking velocity when on the treadmill. Treadmill velocity in session will be guided by baseline data from the Ten Metre Walk Test providing an average comfortable walking velocity in metres per second. For safety and the fact that no weight bearing harness will be employed during the intervention, patients will be advised to use the treadmill handrails for support when required. There is a stationary handrail in front of the participant where individual hands or both hands can be placed and individual stationary handrails for single hand placement on the left and right sides. The participant will also be provided with contact-guard assistance throughout each mirror and treadmill session. Patients will be asked to wear dark sports leggings so that the non-paretic leg can be fully viewed by rolling the fabric above the knee joint and the paretic limb is kept completely covered by the sports leggings to assist in appropriate mirror visual feedback of the non-paretic limb.

Experimental participants will walk on the treadmill while viewing a reflection of their non-paretic limb in a custom built acrylic mirror apparatus, positioned in the mid-sagittal plane between the legs which will provide a full view of non-paretic leg movement, both in rear and forward positions. The angle of the mirror can adjusted according to participant preference to gain a full view of the non-affected limb. Treadmill velocity can increase or decrease according to clinician judgment and participant tolerance. Each session will be divided into two 15-minute sessions with a 5-minute rest period between them. Additionally, according to the Borg RPE Scale comfortable exertion occurs at 13/14 and the participants will asked to let it be known if they experience feelings of 'very hard' while walking. At this point, the participant was encouraged to slow down or take a break.

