Cover Page

Statistical Analysis Plan

Study Title: Mirror Therapy and Treadmill Training for Patients with Chronic Stroke. A Pilot Randomised Controlled Trial

Document creation date: December 12th 2014

NCT number [not yet assigned].

Identifiers: [NCT ID not yet assigned]

Statistical Analysis Plan for Mirror Therapy and Treadmill Training ([name], IT Sligo, Ireland).

All data was analysed using IBM SPSS Statistics 23 for Windows. Conformity to the normal distribution of variables was tested using a combination of the Shapiro-Wilk test and visual assessment (histograms). Demographic characteristics and outcome variables are described as mean ± SD. Groups were compared at baseline using the independent samples t-test for the continuous variables, and the chi-square test for categorical data. Intention-to-treat analysis was used and patients were excluded from a given analysis if their corresponding measurement was missing. The paired samples t-test and the Wilcoxin signed rank test were used to analyse within-subject differences (T1 vs T2 vs T3). Between-subject differences (MT vs PL) were analysed using the independent samples t-test and the Mann-Whitney U test. The interaction of group and time determined the effectiveness of mirror therapy on outcome measures. All tests were conducted on a 5% significance level. Effect sizes for non-parametric tests were calculated using r. Effect sizes for parametric tests were calculated using Cohens's d for within-group analysis and r for between group analysis. Cohens d values of 0.2, 0.5, and 0.8 were interpreted as small, medium, and large respectively; r values of 0.1, 0.3, and 0.5 were defined as small, medium and large.

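### With 30 patients and no stated allocation method, the SAP specifies no baseline adjustment; under unstratified 1:1 allocation the arms would differ by over 0.5 SD in baseline walking speed about 17–18% of the time

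*Protocol*

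**What the plan says.** **Allocation and population (Protocol, opening paragraph and title).** "A total of 30 participants will be randomly assigned to one of two conditions". Nothing is said about the ratio, how the sequence is generated, blocking, stratification or minimisation. No eligibility criteria appear; the population is known only from the title, "Mirror Therapy and Treadmill Training for Patients with Chronic Stroke".

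**Role of baseline speed (Protocol, treadmill paragraphs).** "Treadmill velocity in session will be guided by baseline data from the Ten Metre Walk Test". Patients also guide the speed verbally at each of the 12 sessions, and "Treadmill velocity can increase or decrease according to clinician judgment and participant tolerance".

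**Analysis (SAP, single unnumbered section).** For baseline: "Groups were compared at baseline using the independent samples t-test for the continuous variables". For the treatment comparison: "Between-subject differences (MT vs PL) were analysed using the independent samples t-test and the Mann-Whitney U test". The SAP also makes the group-by-time interaction the criterion for effectiveness, but gives no model for it. It names no covariate, and it does not say whether the between-arm tests use follow-up scores or changes. Neither document lists the outcome measures.

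**The concern.** Comfortable walking speed is measured before training and is likely to predict any gait outcome. It is also the one baseline measurement named as a guide to treatment. Yet the documents give it no role in allocation or in the between-arm analysis. With about 15 patients per arm, a sizeable chance difference on it is not rare.

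Baseline significance tests do not help: they neither correct an imbalance nor reliably detect one at this size. At stake are the precision of this one small trial and how readily its result can be interpreted. Validity on average over repeated randomisations is not in question.

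**Working it through.** **Inputs from the documents:** 30 patients, two arms, 5% significance level, and the SAP's own scale for d (0.2 small, 0.5 medium, 0.8 large).

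**Assumptions:** allocation about 1:1 and unstratified; baseline speed roughly normal; T1 is baseline; equal SDs at baseline and follow-up; a walking-speed-type outcome whose baseline-to-follow-up correlation ρ is 0.8 (range 0.6–0.9).

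The documents give no effect size, SD or power for the 30, so there is no planned figure to reproduce. No SD of walking speed is needed, because everything below is in SD units.

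**1. Chance of a gap above 0.5 SD.** The standard error of the baseline difference is √(1/n₁ + 1/n₂). For 15:15 it is √(2/15) = 0.365 SD, so the 0.5 SD threshold lies at 0.5/0.365 = 1.369 standard errors.

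| Allocation | SD known (normal) | SD estimated (t, 28 df) |
|---|---|---|
| 15:15 | 17.1% | 18.2% |
| 14:16 | 17.2% | 18.3% |
| 12:18 | 18.0% | 19.1% |
| 10:20 | 19.7% | 20.7% |
| Simple (coin toss) | 17.9% | 18.9% |

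Simulation at 15:15 (200,000 replicates) gave 16.9% with the true SD and 18.1% with the pooled sample SD. A skewed (lognormal) baseline gave about 16%. These figures count both directions; the chance that one named arm is ahead by more than 0.5 SD is about 8.5%. Simple randomisation would also give a split of 11/19 or worse with probability 2 × P(Bin(30, 0.5) ≤ 11) = 20.0%.

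**2. Would the baseline t-test show it?** An observed gap of 0.5 SD at 15:15 gives t = 1.369 on 28 df, p = 0.18. Significance at 5% needs about 2.05 × 0.365 = 0.75 SD.

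**3. Shift caused by a 0.5 SD gap.**

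| Comparison | Formula | ρ = 0.6 | ρ = 0.8 | ρ = 0.9 |
|---|---|---|---|---|
| Follow-up scores | ρ × 0.5 | +0.30 | +0.40 | +0.45 |
| Change or interaction | (ρ − 1) × 0.5 | −0.20 | −0.10 | −0.05 |
| ANCOVA | baseline held fixed | 0 | 0 | 0 |

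A plus sign favours the arm that started faster.

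**4. Precision.** Relative to follow-up scores (variance 1), change scores have variance 2(1 − ρ) and ANCOVA has 1 − ρ².

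- At ρ = 0.8 these are 0.40 and 0.36. ANCOVA therefore saves 1 − 0.36 = 64% against follow-up scores and 1 − 0.36/0.40 = 10% against change scores.
- At ρ = 0.6 the savings are 36% and 20%; at ρ = 0.9 they are 81% and 5%.
- Estimating the slope gives a little back. With one normal covariate and 28 within-arm df, the average inflation is 1 + 1/26 = 1.04. At ρ = 0.8 that turns 0.36 into 0.374, so the net savings are about 63% and 7%.

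**5. What stratification would add.** Splitting near the median speed and balancing the arms within the two strata lowers the chance of a gap above 0.5 SD from about 17% to 2.6% (strata of 16 and 14) or 4.2% (strata of 15 and 15, allocated 8/7 and 7/8).

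**The case against.** **The SAP's effectiveness criterion already uses baseline.** This is the strongest point, and much of it stands. A group-by-time interaction compares changes, so the 0.4 SD shift does not apply to it. At ρ = 0.8 the shift is a quarter as large and runs against the arm that started faster. A reader might infer that a faster arm would produce a spurious mirror effect of 0.4 SD; that holds only if the named tests are run on follow-up scores, which the SAP neither states nor excludes. What remains is that no interaction model is specified and that change scores over-correct.

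**Silence is not a design.** A reader might infer that patients of any walking speed are admitted and that allocation is definitely unstratified. The documents say neither. Eligibility is unreported, and treadmill walking in two 15-minute bouts without a harness presupposes some walking ability. Nor would the width of entry alter the probability: in SD units it is the same for a narrow or a wide range, and a wider one only makes 0.5 SD larger in metres per second.

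**This is ordinary chance imbalance.** That is correct. Valid randomisation allows for it in the type I error, and simple randomisation is legitimate in a pilot. The argument for adjustment is precision and interpretability.

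**Only stratification can equalise training speed.** A reader might infer this, but the baseline test is one guide among several. To the extent that training speed follows baseline speed, a correctly specified adjustment for baseline speed covers that route as well. Stratification also has a price. The mirror makes allocation visible to session staff at a single site. With equally likely blocks of 2 and 4, someone who knows past allocations and guesses the under-represented arm is right 1.5 times in a block of 2 and 2.83 times in a block of 4, which is 4.33/6 = 72%.

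**Conclusion.** The point holds as a gap in the analysis plan together with missing detail on allocation. If allocation is about 1:1 and unstratified, the chance of a gap above 0.5 SD on baseline walking speed is 17–18%, and the planned baseline tests would usually not flag a gap of that size.

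The consequence depends on an analysis the SAP leaves open: about +0.4 SD (0.3 to 0.45) for unadjusted follow-up scores, and about −0.1 SD (−0.2 to −0.05) for change scores or the interaction. These shifts rest on the assumed correlation and on the outcome resembling walking speed, since no outcome is named. The imbalance probability rests on neither.

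The documents do not support a claim of systematic bias or of unrestricted entry, nor do they show that stratification was rejected. Adjustment is worth making because it uses a measurement already planned and improves on either unadjusted analysis, though its margin over change scores is modest and shrinks as the correlation rises.

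**What to change.** **Main change, in the SAP.** Replace the unadjusted between-arm tests and the unspecified interaction with:

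> The arms will be compared at T2 and T3 by ANCOVA (or a repeated-measures model with T2 and T3 as outcomes), with group as the factor, adjusted for the baseline value of the outcome and, where that is a different measure, for baseline Ten Metre Walk Test speed. The adjusted difference will be reported with its 95% confidence interval.

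Keep the baseline table as description, and drop its significance tests as a safeguard against imbalance.

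**Cost:** one or two degrees of freedom, a linear-model assumption to be checked on residuals, and no extra patients, visits or measurements. Unlike a change to allocation, it can still be applied after patients have been randomised; if results have already been seen, it should be labelled as post hoc.

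**Reporting, in the protocol.** State the eligibility criteria, including any on walking ability, the allocation ratio, how the sequence is generated, and how it is concealed.

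**Optional, if enrolment has not begun.** Allocate 1:1 with concealment, stratified by baseline speed at a cut-point fixed beforehand, using larger or varied blocks because short ones are predictable where allocation is visible. The walk test must then come before allocation, two lists are needed, and the stratum or the speed itself should be in the model. With 30 patients, larger blocks are more likely to end incomplete and give up some balance, so this is a judgement and not a requirement.

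### Could treadmill speed be set by different rules in the two arms, so that a mirror effect is really a training-intensity effect?

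*Protocol*

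**What the plan says.** The Protocol is a single short section. Its general text on treadmill sessions refers to patients without naming an arm and makes three statements about pace:

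- Aim: "Patients encouraged to walk at their comfortable walking velocity when on the treadmill".
- Guide: "Treadmill velocity in session will be guided by baseline data from the Ten Metre Walk Test".
- Step at the start of each session: "Patients will verbally guide the speed of the treadmill at the beginning of each of the 12 therapy sessions", with the therapist setting the belt to match.

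The next paragraph opens "Experimental participants will walk on the treadmill while viewing a reflection of their non-paretic limb". After describing the mirror it adds "Treadmill velocity can increase or decrease according to clinician judgment and participant tolerance". It then gives the session structure (two 15-minute bouts with a rest between) and an exertion rule for participants who find walking very hard: "At this point, the participant was encouraged to slow down or take a break".

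Neither document says which arm or arms the adjustment sentence covers, and neither mentions recording belt speed. The SAP compares MT with PL by two-sample tests and judges mirror therapy by the group-by-time interaction. It does not describe what PL patients receive.

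**The concern.** Reading the group-by-time interaction as an effect of the mirror requires that nothing else differs systematically between the arms. Speed is an obvious adjustable part of treadmill training. The therapist who sets it stays beside the participant throughout and can see whether a mirror is in use. If discretion to raise speed belonged to the experimental arm alone, MT patients could be trained harder, and a difference from PL might reflect intensity rather than mirror feedback. With no stated speed record, a reader of the results could not tell. In a trial of 30, a modest shift from such a source could be mistaken for a treatment effect.

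**Working it through.** **1. Do the speed statements conflict?** Taken in order, they give an aim (a comfortable pace), a guide (the baseline walk test), a step at the start of each session (the patient says, the therapist sets) and later movement up or down. Each can be followed without breaking another. The documents give no ranking, but they contain no contradiction.

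**2. Is the adjustment sentence confined to the experimental arm?** There are two readings.

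- *The paragraph covers everyone after its opening sentences on the mirror.* The adjustment sentence is then common to both arms, and there is no asymmetry.
- *The whole paragraph is experimental only.* The two 15-minute bouts and the exertion rule then belong to that arm alone as well. The documents would give no walking time for PL, and no between-arm distance could be calculated.

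Any estimate of extra distance that uses the same bouts for both arms has already adopted the first reading. On either reading, the general text provides for therapist adjustment for all patients.

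**3. Size of a speed gap, if there were one.** The inputs are "each of the 12 therapy sessions" and two 15-minute bouts per session, both from the Protocol.

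12 × 2 × 15 min = 360 min; 360 × 60 = 21,600 s.

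Extra distance = speed gap × 21,600 s. The gaps are assumptions, since the documents give no speeds.

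| Assumed mean gap (m/s) | Extra distance per patient (m) |
|---|---|
| 0.05 | 1,080 |
| 0.10 | 2,160 |
| 0.20 | 4,320 |

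**4. What a resulting outcome shift would do to the test.** Assume 15 per arm (the Protocol gives 30 in total but no ratio), a two-sided 5% t-test and no mirror effect. If unequal speed shifts the outcome by δ SD, the test statistic is noncentral t with 28 degrees of freedom and noncentrality δ × √(15/2) = 2.739δ.

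| Assumed shift δ (SD) | Rejection rate |
|---|---|
| 0.1 | 5.8% |
| 0.2 | 8.3% |
| 0.3 | 12.5% |
| 0.5 | 26.2% |

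For scale, 80% power with 15 per arm needs a true difference of (1.960 + 0.842) × √(2/15) = 1.02 SD by the normal approximation, or 1.06 SD by the t-test.

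Nothing in the documents connects the two tables. They name no outcome, give no standard deviation and mention the Ten Metre Walk Test only as baseline data. The distances therefore cannot be turned into a shift, and the rejection rates illustrate a possibility without estimating it.

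**5. Would a speed record change the result?** Speed is set after randomisation, so it should not enter the model as a covariate; the test and the estimate would stay as they are. A table of speed by arm could show a gap but not its cause. If watching the mirror makes a faster pace comfortable, the gap is part of the mirror's effect, and the randomised comparison rightly includes it. If the therapist pushed one arm harder, it is a co-intervention. The same table would result from either.

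**The case for a change.** The best case for acting is that the remedy is cheap: one clause stating which arms the adjustment sentence covers, two entries on a session log and one descriptive table. The therapist is not blind to the mirror, and the Protocol states neither a limit on adjustment nor a requirement to keep progression equal. In a pilot, delivered dose is also useful for planning a later trial.

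Much of this stands. The scope of the sentence is unstated, recording is unstated, and therapist behaviour could differ by arm even if the sentence is general. But that last risk comes from an unblinded therapist with discretion over speed. A clarifying clause would not remove it, and the table would describe a gap without explaining it. Both arms' speeds are also tied to each patient's own baseline pace and comfort, which limits arbitrary divergence. The absence of any account of what PL patients do is a real and broader omission, but it is a separate point from the speed wording.

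**Conclusion.** The plan needs no change on this point. The speed statements are compatible, and an experimental-only speed rule is one possible reading that the neighbouring sentences make less likely. What is left is missing detail that the trial team can fill sensibly: the arms covered by one sentence, and whether belt speed is logged. The documents show that training intensity could differ between arms, not that it would.

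The figures of 1,080 to 4,320 m rest on assumed gaps of 0.05 to 0.20 m/s and on equal walking time in both arms. The rejection rates of 5.8% to 26.2% rest on assumed shifts of 0.1 to 0.5 SD and on 15 per arm. None of these assumed gaps or shifts is supported by the documents. Reporting delivered speed by arm would be good practice in a pilot, but it would leave the planned tests and their estimates as they are. How speed should be set is a clinical matter for the investigators.

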Cover Page

Statistical Analysis Plan

Study Title: Mirror Therapy and Treadmill Training for Patients with Chronic Stroke. A Pilot Randomised Controlled Trial

Document creation date: December 12th 2014

NCT number [not yet assigned].

Identifiers: [NCT ID not yet assigned]

Statistical Analysis Plan for Mirror Therapy and Treadmill Training ([name], IT Sligo, Ireland).

All data was analysed using IBM SPSS Statistics 23 for Windows. Conformity to the normal distribution of variables was tested using a combination of the Shapiro-Wilk test and visual assessment (histograms). Demographic characteristics and outcome variables are described as mean ± SD. Groups were compared at baseline using the independent samples t-test for the continuous variables, and the chi-square test for categorical data. Intention-to-treat analysis was used and patients were excluded from a given analysis if their corresponding measurement was missing. The paired samples t-test and the Wilcoxin signed rank test were used to analyse within-subject differences (T1 vs T2 vs T3). Between-subject differences (MT vs PL) were analysed using the independent samples t-test and the Mann-Whitney U test. The interaction of group and time determined the effectiveness of mirror therapy on outcome measures. All tests were conducted on a 5% significance level. Effect sizes for non-parametric tests were calculated using r. Effect sizes for parametric tests were calculated using Cohens's d for within-group analysis and r for between group analysis. Cohens d values of 0.2, 0.5, and 0.8 were interpreted as small, medium, and large respectively; r values of 0.1, 0.3, and 0.5 were defined as small, medium and large.

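### The SAP claims intention-to-treat but deletes patients test by test; if any value is missing, the affected analysis is at best available-case by allocated group (minor)

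*SAP*

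**What the plan says.** The SAP is a single unnumbered section. On the analysis population and missing data it has one sentence: "Intention-to-treat analysis was used and patients were excluded from a given analysis if their corresponding measurement was missing".

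The tests it names are:
- within arm: "The paired samples t-test and the Wilcoxin signed rank test were used to analyse within-subject differences (T1 vs T2 vs T3";
- between arms: "Between-subject differences (MT vs PL) were analysed using the independent samples t-test and the Mann-Whitney U test".

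The criterion for benefit is separate: "The interaction of group and time determined the effectiveness of mirror therapy on outcome measures". No model or test is attached to that interaction.

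The Protocol gives the denominator: "A total of 30 participants will be randomly assigned to one of two conditions". It does not mention missing data.

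Neither document defines intention-to-treat, says that patients are analysed in the arm allocated, gives an expected loss, or plans imputation, a likelihood method, a missing-data sensitivity analysis or a report of numbers analysed. T1, T2 and T3 are not defined; I read them as baseline and two later assessments.

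**The concern.** A reader who sees the intention-to-treat label will normally take it that everyone randomised was analysed. The second half of the same sentence removes patients whenever a value is absent. The rule is disclosed, and the label may mean only that patients are kept in their allocated arm, but the SAP does not say so.

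Two things are at stake. One is accurate description: with 30 patients, a few missing values change the denominator visibly, and no table of denominators is planned. The other is possible bias: if loss before T3 is related to how a patient did between T1 and T2, a comparison restricted to those seen at T3 can be off, and the named tests have no means of using the observed T2 value to correct it.

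**Working it through.** **Step 1. Label against rule.** The plan derives no figure on this point, and 30 comes without a power calculation, so there is nothing to reproduce. For a patient seen at T1 and T2 but not T3:

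| Analysis | Patient included? |
|---|---|
| Paired test T1 v T2 | yes |
| Between-arm test at T2 | yes |
| Paired tests T1 v T3, T2 v T3 | no |
| Between-arm test at T3, or on T1–T3 change | no |
| Group-by-time interaction | unknown: a complete-case repeated-measures ANOVA drops the patient, a mixed model does not |

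The analyses in the third and fourth rows then have fewer than 30 patients.

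**Step 2. Assumed inputs (none are in the documents).** 15 patients per arm; outcome SD 1 at each time; equal correlation ρ of 0.8 or 0.6 between times; loss at T3 only, 12% or 24% in each arm; in one arm the log-odds of loss change by 1 per SD of the T1–T2 change, and in the other arm loss is random. Patients left at T3: 30 × 0.88 = 26.4 or 30 × 0.76 = 22.8.

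**Step 3. Bias, loss depending on progress in one arm.** The T1–T2 and T1–T3 changes each have variance 2(1−ρ) and their covariance is 1−ρ, so the regression slope of one on the other is 0.5. Let σ = √[2(1−ρ)], which is 0.632 or 0.894. With p the loss probability and L its mean, the standardised T1–T2 change among retained patients shifts by s = E[p(1−p)]/(1−L). Numerical integration gives:
- L = 12%: s = 0.0948/0.88 = 0.108
- L = 24%: s = 0.156/0.76 = 0.205

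Bias = 0.5 σ s. Standard error = σ√{2/[15(1−L)]}.

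| Loss | ρ | Bias (SD) | Standard error (SD) |
|---|---|---|---|
| 12% | 0.8 | 0.034 | 0.25 |
| 12% | 0.6 | 0.048 | 0.35 |
| 24% | 0.8 | 0.065 | 0.26 |
| 24% | 0.6 | 0.092 | 0.37 |

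Simulated type I error of the available-case t-test (40,000 trials per setting) was 5.1–5.7%. With complete data or random loss the bias is 0.

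**Step 4. Same loss rule in both arms.** The bias is 0.5 σ (s₁ − s₀), where s₁ and s₀ are the shifts in the two arms. These differ only if the mean T1–T2 change differs between arms, that is, if an effect is already present at T2. For an effect of 0.5–0.8 SD at both T2 and T3, the bias is −0.02 to −0.03 SD at 12% average loss and −0.03 to −0.05 SD at 24%, towards zero whichever way loss runs. With no effect, or one that appears only at T3, it is 0.

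**Step 5. Other assumptions.**
- Autoregressive correlation, one arm: 0.06–0.08 SD at 12% and 0.12–0.15 at 24%.
- Opposite loss rules in the two arms at 24% (a stress case): 0.13–0.18 SD, type I error 7.3–7.6%.
- T3 values compared instead of change, loss depending on the T2 value in one arm: 0.065–0.086 SD at 12% and 0.123–0.164 at 24%. If loss depends on T1–T2 change: 0.00–0.06.

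**Step 6. What a mixed model would gain.** REML with unstructured covariance and Satterthwaite degrees of freedom had bias of at most 0.005 SD when loss depended on observed data. Root mean squared error in the one-arm cases fell from 0.248 to 0.244 and from 0.351 to 0.344 at 12%, and from 0.273 to 0.263 and from 0.387 to 0.369 at 24%, a gain of about 2–5%. Its type I error reached about 5.9% in these observed-data settings, the highest value being in the stress case. When loss depended on the unseen T1–T3 change in one arm (24%), bias fell only from 0.128 to 0.094 (ρ = 0.8) and from 0.185 to 0.130 (ρ = 0.6), with type I error up to about 7.2%.

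**The case against.** The other side has a good deal. No missing data are shown: neither document gives a loss rate or a mechanism. The 12 sessions in the Protocol are therapy sessions, not assessments, so they say little about missed measurements. The emphasis on T3 is mine: no primary time point is named, and if loss occurs only at T3 the T1–T2 contrast is complete and none of the bias figures apply. Under the plainer assumptions the bias is well below one standard error and the mixed model gains little. For a 30-patient pilot, a model for every outcome can look like preference. All of this stands, and it is why the point is minor.

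Three stronger readings are tempting, and the documents do not support them:
- *That T2 data are thrown away when T3 is missing.* Exclusion is per analysis, so the patient still counts wherever only T1 and T2 are needed. What is lost is the use of T2 to inform T3.
- *That the effectiveness analysis is complete-case.* The interaction has no named model. A mixed model also omits missing records while keeping the patient's other visits, so the exclusion rule does not rule one out.
- *That selective loss always dilutes a true effect.* Under a common loss rule driven by T1–T2 change, this needs an effect already present at T2.

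What the objection does not remove is the label. It is inaccurate for any analysis with a missing value, and the SAP plans no count that would let a reader see this.

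**Conclusion.** The point holds conditionally and is minor. If every measurement is present, the exclusion rule does nothing. If any is missing, the affected analysis is available-case, by allocated group at best, because the SAP never states that patients are analysed as allocated. The t and rank tests do not carry T2 information to T3; for the interaction this cannot be told.

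Under the main assumed scenario the likely harm is a modest bias, not a material rise in false positives. Larger figures arise only under less favourable assumptions: autoregressive correlation, opposite loss rules by arm, a comparison of T3 values, or loss driven by unseen values. The sizes rest wholly on assumed loss, correlation, equal allocation and mechanism. A reader might infer that the trial's result is biased; nothing in the documents shows that.

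**What to change.** 1. **Relabel.** Describe every analysis that keeps per-test deletion, including the rank tests, as available-case by allocated group, and confirm that patients are analysed in the arm to which they were randomised. Cost: one sentence.
2. **Report denominators.** Give the number analysed per arm at T1, T2 and T3 for each outcome. Cost: one table, useful even if the analysis is finished.
3. **Name the interaction model.** For approximately normal outcomes, estimate group-by-time in one REML mixed model (SPSS MIXED, unstructured covariance, Satterthwaite degrees of freedom). Include every randomised patient with at least one measurement, in the allocated arm. State whether the interaction is the overall test or a named contrast such as T1–T3. The SAP already specifies SPSS, so this is one run per outcome. The SAP is written in the past tense ("All data was analysed using IBM SPSS Statistics 23 for Windows"); if the analysis is done, report the model as a post hoc sensitivity analysis, not as a replacement.
4. **If T3 values are missing, add one shift analysis.** Move the missing T3 values in one arm by a stated amount. For example, 3 of 15 missing and a shift of 0.5 SD moves the arm difference by 3/15 × 0.5 = 0.10 SD.

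Downsides: the model assumes data missing at random and approximate normality, which 30 patients can hardly check. It removes only about a quarter to a third of the bias when loss depends on the unseen T3 result, hence item 4. It offers no real type I advantage outside the stress cases. Rank-tested outcomes gain only the correct label.
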